It is proposed to randomly assign at least 100 patients sequentially based on admission; in a single blind, interventional trial, to two separate groups. Patients are going to be selected from our university teaching hospital. patients were randomly assigned to a study group with the use of permuted blocks and stratification using well trusted randomization websites or software programs (SAS). Permuted block randomization list will be transferred from alphabetic symbol by the competent orthopedic supervisor and coded based on the randomization order by manual coding preset by orthopedic supervisor [5]. Double dummy technique may be feasible here as long as we tackled difficulty of providing syringes containing saline. However, the risk of injecting a saline solution subcutaneously (i.e. bleeding complications may develop in persons taking an anticoagulant agent plus unnecessary injections) may outweigh the benefit. Since the investigator do not know which therapy is administrated, the potential for the results to be biased is minimized [6].

The first group is to be on rivaroxaban with dosage according to the orthopedic approved regimen (10 mg once daily 6-10 hours after the surgery; recommended total duration of therapy: 12 to 14 days; ACCP recommendation: Minimum of 10 to 14 days; extended duration of up to 35 days suggested (Guyatt 2012).[3]

The other group will be administered the standard of care (SOC) enoxaparin. Dosage and duration of therapy are illustrated in Table 1 [2].

Drug	Dosage and Duration
Enoxaparin	Once-daily dosing: 40 mg once daily, with initial dose within 9 to 15 hours before surgery, and daily for at least 10 days (or up to 35 days postoperatively) or until risk of DVT has diminished or the patient is adequately anticoagulated on warfarin. The American College of Chest Physicians recommends initiation ≥ 12 hours preoperatively or ≥ 12 hours postoperatively; extended duration of up to 35 days suggested (Guyatt, 2012).

Table 1: *Dosing of SOC drugs used in thromboprophylaxis after orthopedic surgery.*

It is expected here that all medication will be taken for a duration of 10 days after surgery. The type, duration and dose of the thromboprophylactic agents will be discussed with and determined by the competent physician before saying a particular patient can be enrolled.

Study population

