The primary efficacy outcomes are the composite of any deep-vein thrombosis, nonfatal pulmonary embolism, or death up to 30 days. The main secondary efficacy outcome is major venous thromboembolism, which is defined as the composite of proximal deep-vein thrombosis, nonfatal pulmonary embolism, or death from venous thromboembolism.

The main safety outcome is the incidence of major bleeding beginning after the first dose of the study drug and up to 2 days after the last dose of the study drug (on-treatment period). Major bleeding is defined as bleeding that is fatal, occurs in a critical organ (e.g., retroperitoneal, intracranial, intraocular, and intraspinal bleeding), or requires reoperation or extra surgical-site bleeding that was clinically overt and is associated with a fall in the hemoglobin level of at least 2 g per deciliter or that requires transfusion of 2 or more units of whole blood or packed cells. Other safety outcomes include any on-treatment bleeding, any on-treatment non- major

bleeding, hemorrhagic wound complications (a composite of excessive wound hematoma and reported surgical-site bleeding), any bleeding that starts after the first oral dose of rivaroxaban and ended up to 2 days after the last dose is administered, adverse events, and death.

Validated clinical prediction rule is recommended to estimate pretest probability of venous thromboembolism. Duplex ultrasonography is the preferred test to diagnose DVT [7]. Many prediction scales are available like *Wells Clinical Models for Evaluating the Pretest Probability of VTE*.

Symptoms and signs of DVT may include unilateral leg swelling, pain in the affected leg, calf tenderness in affected leg, increased leg warmth, erythema of affected leg, or a “palpable cord” may be felt in the affected leg.

Regarding PE, diagnosis is suspected in patients with dyspnea, tachypnea, pleuritic chest pain, cough, and/or fever. Diagnosis begins with initial risk stratification based on presence of shock or persistent hypotension to identify patients at high risk of early mortality.

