For patients with suspected high-risk PE with shock or hypotension, emergency computed tomography(CT) angiography beside transthoracic echocardiography is recommended depending availability and clinical circumstances. While for patients not suspected of having high-risk PE, clinical assessment of likelihood of PE using validated prediction rules and clinical judgement to distinguish between low and high-risk PE may use [8]. However, PE can be diagnosed based on computed tomography pulmonary angiography (CTPA). CT pulmonary angiography is preferred method when available.

It is recommended to have baseline Scr and platelets count. Based on Heparin induced thrombocytopenia, it is advisable to monitor platelets count beginning of the fourth day and every three days until discontinue of Heparins.

Data analysis

The patients in the two groups will be matched in advance for the difference in Patients’ characteristics, VTE risk factors, history of VTE, types of surgery, types of anesthesia and duration of surgery. This ensures fair randomization between groups. Statistical analysis will be performed at an overall significance level of 0.05, adjusted for the primary and secondary end points using non- independent t-test

(SPSS software). Comparisons of the primary end points between treatment groups were performed by means of a log-rank test. To estimate the size of the effect, we will use a Cox regression model. On the other hand, the cost-effective analysis (CEA) will be based mainly on estimating the average cost-effective ratio(ACER) and the incremental cost for each additional cure.

References

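### The plan names a non-independent t-test as its adjustment for the overall 0.05; that test adjusts nothing, competes with the log-rank test for the primary, and is the only test named for major VTE

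*Combined protocol and SAP*

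**What the plan says.** All points are in the combined protocol and SAP.

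- **Error rate and t-test (Data analysis).** The analysis runs at an "overall significance level of 0.05, adjusted for the primary and secondary end points using non- independent t-test", in SPSS.
- **Log-rank and Cox (Data analysis, next two sentences).** "Comparisons of the primary end points between treatment groups were performed by means of a log-rank test". A Cox model then estimates the size of the effect, with no endpoint named.
- **Matching (start of Data analysis).** "The patients in the two groups will be matched in advance for the difference in" a list of characteristics that ends with "types of surgery, types of anesthesia and duration of surgery". The stated purpose is fair randomisation.
- **Endpoints (Outcome measure and follow up).** The primary is the "composite of any deep-vein thrombosis, nonfatal pulmonary embolism, or death up to 30 days". "The main secondary efficacy outcome is major venous thromboembolism", itself a composite of events.
- **Allocation (Study design and randomization).** The trial will "randomly assign at least 100 patients sequentially based on admission", and "patients were randomly assigned to a study group with the use of permuted blocks and stratification".

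No per-endpoint alpha, testing order, multiplicity procedure or sidedness is given.

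**The concern.** There are three faults in two adjoining sentences.

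1. **Nothing is adjusted.** A t-test compares means. It does not share 0.05 between endpoints or order them.
2. **The primary has two tests.** The t-test clause covers primary and secondary endpoints; the log-rank sentence covers the primary. Nothing says which one decides.
3. **Major VTE has only the t-test.** The log-rank sentence stops at the primary, and the Cox sentence concerns estimation.

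The natural reading of non-independent is paired. A paired t-test needs a defined partner for each patient and a difference that is reasonable to average. Here the outcomes are yes/no or time-to-event, and patients are randomised individually.

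Two analysts following the text could report different primary p-values. The p-value for major VTE could depend on the order of rows in the data file.

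**Working it through.** **1. Are there pairs?** The matching sentence is the only possible source. Against it:
- patients are allocated in order of admission by permuted blocks;
- no rule for forming pairs and no pair identifier is described;
- duration of surgery is known only after the operation, while Table 1 allows enoxaparin to start before it, so pairs matched on that factor cannot exist before treatment.

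The sentence therefore reads as a hope for balance. Even true pairs with yes/no outcomes would call for a method for paired binary data.

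**2. Row-order effect.** Assumed counts: 8/50 against 2/50 (the plan gives no event rates or allocation ratio; 50 per arm is half of 100). Let k be the number of rows with an event in both arms.

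- Mean difference = (8 − 2)/50 = 0.12 for every k.
- Sum of squared differences = (8 − k) + (2 − k) = 10 − 2k.
- Variance = (10 − 2k − 50 × 0.12²)/49 = (9.28 − 2k)/49.
- t = 0.12/√(variance/50), on 49 degrees of freedom.
- Under random row order, P(k) is hypergeometric; for example P(0) = (42 × 41)/(50 × 49) = 0.70.

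| k | variance | t | p | probability |
|---|---|---|---|---|
| 0 | 0.189 | 1.95 | 0.057 | 0.70 |
| 1 | 0.149 | 2.20 | 0.032 | 0.27 |
| 2 | 0.108 | 2.58 | 0.013 | 0.02 |

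The same patients and outcomes fall on either side of 0.05. Other tests on these counts:

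| Test | p |
|---|---|
| Log-rank, over all 45 orderings of the ten events | 0.041 to 0.053, median 0.047 |
| Independent t-test | 0.046 |
| Chi-square, uncorrected: 100 × (8 × 48 − 2 × 42)²/(10 × 90 × 50 × 50) = 4.0 | 0.046 |
| Fisher exact | 0.092 |

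**3. Can the stated 0.05 be reproduced?** No; the plan gives no rule from which to derive it. Two independent tests at 0.05 give 1 − 0.95² = 0.0975. For correlated normal statistics, two-sided, the error is 0.0951, 0.0907, 0.0835 and 0.0704 at correlations 0.3, 0.5, 0.7 and 0.9.

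**4. Family-wise error for this design.** Simulation with no true difference: 50 per arm, 40,000 replicates per setting, uniform event times to day 30, no dropout, and each endpoint tested at 0.05. Major VTE is taken as 20%, 40% or 60% of primary events; ranges are over those fractions.

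| Assumed primary event rate | Log-rank primary, paired t secondary | Log-rank for both |
|---|---|---|
| 1% | 0.2% | 0.2% |
| 2% | 1.4% | 1.4% |
| 5% | 4.6–6.1% | 4.6–6.0% |
| 10% | 6.1–8.3% | 6.1–8.2% |
| 20–40% | 7.6–9.2% | 8.0–9.5% |

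An exact calculation with uncorrected chi-square for both endpoints agrees: 0.2%, 1.3–1.4%, 4.5–6.0%, 6.1–7.9% and 8.5–9.6%.

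The columns are nearly equal, so the excess comes from having no testing rule and not from pairing. The paired t-test alone has size 4.2% to 5.4% at event rates of 5% to 40%.

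**5. With a testing rule.** If major VTE is tested only after a significant primary, the error with no true difference is the primary's own level: 4.8% to 5.1% at event rates of 10% to 40%.

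**The case against.** - **Non-independent may be a slip for independent.** This is possible, and the row-order effect would then vanish: on the example counts the independent t-test and the chi-square test both give 0.046. The effect would also vanish if real pairs existed. Neither reading supplies an adjustment or settles which test decides the primary, and a t-test would still be the only test for major VTE.
- **The t-test phrase may attach to the analysis and not to the adjustment.** Then the adjustment method is simply unnamed. The overall 0.05 is still not secured.
- **The specific log-rank sentence may govern the primary.** That is probably the intent and makes the conflict easy to resolve, but the text does not say so. It leaves major VTE and the overall level untouched. Cox may be meant for major VTE too, but only as estimation.
- **Inflation is not shown.** This stands in part. It depends on an event rate that the plan omits, and at 1% to 2% the error is far below 5%. The example counts lie close to 0.05, where tests often disagree. The figures show what the wording permits, not what will happen.
- **Log-rank may not be ideal.** If thrombosis is found mainly by imaging at a fixed visit, event times largely reflect visit dates. This is a fair reason to report a risk difference as well, but not a reason to keep the t-test.
- **Fixed sequence is a choice.** True. A split of 0.025 + 0.025 = 0.05 also holds the overall level.

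**Conclusion.** The concern holds and must be fixed before any analysis. Three conclusions rest on the text alone: no procedure secures the overall 0.05, the primary has two named tests, and major VTE has only a t-test, which does not fit an event composite.

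The sizes rest on assumptions. The row-order effect requires the literal paired reading, no real pairs and the example counts. The family-wise figures assume 1:1 allocation, 50 per arm, no dropout and the stated event rates; they run from 0.2% at a 1% rate to about 9.5% at 20% to 40%. Pairing does not itself inflate the error.

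**What to change.** In Data analysis:

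1. Delete the t-test wording and state that no matched pairs are analysed.
2. Name one primary test: a two-sided log-rank test at 0.05 on the 30-day composite, with the Cox hazard ratio and its 95% confidence interval.
3. Use the same log-rank method for major VTE, at 0.05 and only if the primary is significant. State its time window, since the 30-day limit is attached only to the primary, and censor at death from other causes.
4. Report safety and other outcomes with 95% confidence intervals and without significance claims.
5. Stratify the log-rank test only by factors that the protocol names and uses in the randomisation.
6. Optionally, add the 30-day risk difference with a score or exact 95% confidence interval. It remains usable if one arm has no events and does not depend on visit timing within the window.

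The cost is a few sentences, with no new data or patients. The downside is that major VTE cannot be claimed if the primary is not significant. If that is unacceptable, a prespecified 0.025/0.025 split avoids it, at the price of a stricter primary test.

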Moreover, very few randomized clinical trials (RCTs) are powered to study side effects when comparing substances, and even large RCTs may be too small to reveal rare side effects. It seems difficult to compare safety data from trial to trial because there is no standardized definition of bleeding. One prospective study collecting data from the electronic health record at two institutions concluded that using of enoxaparin for VTE prophylaxis following THA and TKA was associated with a lower rate of the primary outcome (any postoperative bleeding) compared with the use of rivaroxaban in a similar cohort of patients. However, it was a retrospective investigation with many limitations can be argued with regard to selection and change in practice guideline during the study period.

Finally, there is lack of literature data that define rivaroxaban as orthopedic postoperative thromboprophylactic agent rather than well-known indications (hip and knee replacements). It also is not plausible to accurately compare safety data with other injectable anticoagulants.

Aim of the work

The main objective is to reduce the incidence of venous thromboembolism (VTE) in orthopedic postoperative patients based on the potential benefit of using rivaroxaban as a monotherapy.

It is around efficacy and safety evaluation of using rivaroxaban as a monotherapy prophylactic agent in patients undergoing orthopedic surgeries taking into the account the reliable selection of patients most benefit.

Answering questions about additional cost benefit from the perspective of the cost-effective analysis on extrapolating the results emerged to our university teaching hospital setting are going to be evaluating as well.

Methodology

Study design and randomization

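### The cost-effectiveness analysis pairs the ACER with an incremental cost per cure and does not say which decides; the ACER holds no between-arm contrast, and no trial outcome is a cure

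*Combined protocol and SAP*

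**What the plan says.** The aims include an economic question for the teaching hospital: "Answering questions about additional cost benefit from the perspective of the cost-effective analysis" (Aim of the work). The whole method is one sentence in Data analysis: the analysis "will be based mainly on estimating the average cost-effective ratio(ACER) and the incremental cost for each additional cure". Both quantities stand under the same word, mainly, and neither is ranked above the other.

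The outcome section lists events, not cures: "The primary efficacy outcomes are the composite of any deep-vein thrombosis, nonfatal pulmonary embolism, or death up to 30 days". The secondary efficacy and safety outcomes are likewise thromboembolic events, deaths, bleeding and adverse events. Patients enter because prophylaxis has been decided on, not because they have a thrombosis to be cured.

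The documents do not define cure, list cost items, give prices or an expected event rate, set a willingness-to-pay threshold, state a rule for choosing between the drugs, or describe uncertainty around either ratio.

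**The concern.** An ACER is a within-arm ratio: mean cost divided by effectiveness in the same arm. The aim asks what is gained for any additional cost, which is a difference between arms. Setting two ACERs side by side does not supply that difference. In a prophylaxis trial the natural effectiveness measure is the share of patients free of the composite. When that share is high in both arms, dividing by it changes the cost little, and a comparison of ACERs becomes largely a comparison of prices.

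The second quantity is comparative, but its denominator is undefined as written because no outcome is a cure. The plan therefore has one measure that cannot answer the question and one whose unit must be settled later. The two can also point in different directions, and without a stated rule the choice could be made after the data are seen. At stake is the cost conclusion for the hospital. The efficacy and safety comparisons are not affected.

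**Working it through.** The plan gives no ACER, incremental ratio, cost or event rate, so there is no figure of its own to reproduce.

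**Inputs from the documents**
- Sample size: "It is proposed to randomly assign at least 100 patients sequentially based on admission", in two groups.
- Outcome: the 30-day primary composite.

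**Assumptions, because the documents are silent**
- 50 patients per arm (the allocation ratio is not stated).
- Effectiveness is the share free of the composite.
- The lower ACER is preferred. The plan does not state this rule.
- *p* is the event risk on the dearer drug, and the cheaper drug doubles it to 2*p*.
- *r* is the cheaper drug's cost divided by the dearer drug's cost.
- *k* is the cost of one event, in multiples of the dearer drug's cost; *k* = 0 means drug-only costs.

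**Step 1: how far the ACER moves when events double.** With the dearer drug's cost set to 1, ACER = (drug cost + *k* × risk) / (1 − risk). With *k* = 0, doubling the risk multiplies an arm's ACER by (1 − *p*)/(1 − 2*p*).
- *p* = 1%: 0.99/0.98, a rise of 1.0%
- *p* = 5%: 0.95/0.90, a rise of 5.6%
- *p* = 10%: 0.90/0.80, a rise of 12.5%
- *p* = 20%: 0.80/0.60, a rise of 33%

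The insensitivity is marked at low risks and disappears at high ones.

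**Step 2: break-even price.** In expectation, the cheaper drug with doubled events has the lower ACER when *r* < (1 + *kp*)(1 − 2*p*)/(1 − *p*) − 2*kp*. At *p* = 5%:
- *k* = 0: 0.90/0.95 = 0.947, so a discount just over 5% is enough.
- *k* = 5: 1.25 × 0.947 − 0.50 = 0.684, so a discount of about 32% is needed.
- *k* = 10: 1.50 × 0.947 − 1.00 = 0.421, so a discount of about 58% is needed.

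**Step 3: probability in a trial of this size.** The chance that the cheaper, worse drug shows the lower observed ACER is the exact sum over two independent binomials with 50 patients each.

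| Risk, cheaper v dearer | Event cost *k* | 5% cheaper | 10% cheaper | 20% cheaper |
|---|---|---|---|---|
| 10% v 5% | 0 | 0.51 | 0.78 | 0.995 |
| 10% v 5% | 5 | 0.22 | 0.22 | 0.35 |
| 10% v 5% | 10 | 0.22 | 0.22 | 0.22 |
| 20% v 10% | 0 | 0.24 | 0.44 | 0.88 |
| 40% v 20% | 0 | 0.03 | 0.08 | 0.31 |

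For 10% v 5% with *k* from 3 to 10 and the drug 10% to 30% cheaper, the range is 0.22 to 0.66.

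**Step 4: the two planned measures side by side.** Take 10% v 5%, *r* = 0.8, *k* = 0. The ACERs are 0.8/0.90 = 0.889 for the cheaper drug and 1/0.95 = 1.053 for the dearer, so the ACER ranks the cheaper drug first. The incremental ratio is (1 − 0.8)/(0.10 − 0.05) = 4.0: each extra event-free patient costs four times the dearer drug's price. Whether that is worth paying is a matter of judgement. The incremental ratio shows the trade-off and the ACER hides it.

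**The case against.** The strongest reply is that the comparative measure is already planned. A reader might infer that the analysis rests mainly on the ACER, but mainly governs both quantities, so the text does not support that. Nor does the plan say that the lower ACER picks the drug. That rule is assumed here, and every probability above depends on it. Both points stand. They leave open which measure decides and what its unit is.

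A reader might also infer that the ACER would usually favour a cheaper drug even when that drug doubles events. This holds only for low event rates, drug-only costs and a clear price gap. At 10% v 5% with a 5% price gap it is close to a coin toss (0.51); at 20% v 10% with a 10% gap it is 0.44; and with event costs counted it can be as low as 0.22. The documents list no cost items, and the composite counts any deep-vein thrombosis, so neither event costs nor a higher event rate can be ruled out.

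Finally, if the drugs truly do not differ in effect, favouring the cheaper one is the correct answer and is no evidence of a fault.

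None of this makes the ACER a between-arm measure or gives the word cure a meaning in this trial.

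**Conclusion.** The point holds in a limited form. The plan uses the ACER as one of two unranked bases for its cost conclusion, although the ACER cannot answer the between-arm aim, and it expresses the other in a unit that matches no outcome. Both facts follow from the text without assumed inputs.

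How far this could mislead is conditional. With the assumed rule, 50 per arm and drug-only costs, the probability of ranking first a drug that doubles events from 5% to 10% runs from about 0.51 to 0.995 as its discount goes from 5% to 20%. It is lower with higher event rates or with event costs included. The documents do not show which of these settings applies. The plan should be changed, but the matter is confined to a secondary economic aim.

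**What to change.** Replace the sentence on cost-effectiveness in Data analysis with text to this effect:

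*Mean cost and the 30-day risk of the primary composite will be reported by arm. The between-arm conclusion will rest on the incremental cost and the incremental number of primary composite events avoided (rivaroxaban minus enoxaparin), shown jointly with their uncertainty, for example from a bootstrap that resamples patients within arm. Any ratio will be expressed per additional primary composite event avoided. Average cost-effectiveness ratios are descriptive and will not be used to choose between arms.*

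The plan should also list the cost items, in particular whether the cost of treating events is counted, since the working shows how strongly the ratios depend on it.

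The change is to wording and analysis; the ratios already need the same cost and outcome data. The price is that the simple single-number ranking is lost and the cost conclusion will look less certain. With about 50 patients per arm, that uncertainty is real and should be shown.
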